3.3 Study design

This is a national single-centre, two-arm, open labelled randomised controlled trial within the stroke units and stroke centres of the swiss stroke registry in a superiority fashion.

3.3.1 Potential problems associated with the trial desing

As no blinding of the surgeons or the patients is possible, potential bias can occur in this trial. Furthermore, the Hawthorne effect could be observed since the patients are aware of which treatment arm they received.

3.3.2 Methods of minimising bias

We plan to enrol a large enough sample to eliminate random error. Randomisation in 1:1 fashion should reduce any selection bias of patients due to the treating physician's expectation and possible confounders are well distributed among the groups. Randomisation will be done using a CDMS (SecuTrial®) by a trained member of the study personnel. All study personnel will be trained and instructed for the study procedures. The primary outcome evaluation is performed by blinded study personnel via telephone interviews, the primary outcome analysis is performed by our blinded trial statistician not involved the treatment plan of the patients. Other forms of reducing bias will be the use of prospective CRF Forms, the use of validated and commonly applied scores (mRS/NIHSS/GCS/PROMIS®/MOCA) for the outcome assessments and blinded laboratory personnel assessing the biomarker results, as the individuals analysing the biomarkers will have no information regarding the treatment plan of the patient. Lastly, regular quality control will take place to ensure that all procedure standards are met. Explorative stratified sub-group analysis accounting for possible confounders mentioned in 3.2 will be conducted.

3.3.3 Randomisation

Each eligible patient will be allocated to either the early ES or the BMT group in a 1:1 fashion, stratified for centre and with variable block length. This process will take place 1) after enrolment criteria were met, 2) the patient gave his/her consent or, if the patient is not able to consent, an independent physician confirmed that the interests of the patient are preserved and 3) within 24 hours after symptom onset have passed. A trained individual of the study team will implement the randomisation procedure within SecuTrial®. The allocation sequence is programmed in our CDMS SecuTrial®, which generates random block randomization algorithms

of variable length for a randomization in a 1:1 fashion. Randomisation is stratified for centre. It will also include a standard minimisation algorithm which will ensure that the treatment groups are balanced. The allocation sequence will be programmed in the CDMS by the data manager and, if necessary, a study-independent statistician. Patient ID and study arm will be generated by the randomization program and disclosed to the treating team electronically. Thus, the treatment allocation is concealed to the study team until randomization is conducted.

3.3.4 Blinding and Unblinding procedures (Code Break)

Since this is a surgical trial, blinding is not possible for primary care providers. However, the laboratory personnel analyzing the biomarkers as well as the statistician will be blinded as these are not directly involved in the patient care or outcome assessment. Laboratory personnel will be blinded to the allocation as only encoded material will be processed where patients are identified by their patient ID, which gives no hint to the allocation. Likewise, the study statistician responsible for the primary analysis will receive a blinded copy of the data sets. Furthermore, we will conduct blinded outcome assessment at 3 and 6-month follow-up through study personnel blinded to the allocation of the patient in form of a standardized telephone assessment (Appendix 4)[35]. This form of assessment is highly comparable with face-to-face evaluation, is short and easy to implement[36].

Since no patient or care provider blinding is possible (due to the study design including a surgical treatment arm), no emergency unblinding is necessary.

3.4 Study intervention

3.4.1 Intervention group

The intervention group will first receive BMT (as described below) upon admission and early minimally invasive image guided endoscopic hematoma evacuation as an add-on therapy to BMT. Surgery will be performed within 6-24 hours after SSICH symptom onset. A detailed standardized presentation of the technique and all critical steps of the surgery including imaging, setup of image guidance and endoscopic equipment, as well as the exact process of aspirating the clot will be provided to all involved surgeons by a proctored workshop. Additionally, we published a technical note describing the technique with a video illustrating the steps of the surgery[37]. All individual parts of the procedure are standard neurosurgical practice. Regular training will be conducted to maintain and improve adherence.

The initial cCT scan or in case surgery is delayed more than 6 hours after the initial scan, a second cCT scan (stability scan), will be used for presurgical planning of the neuro-navigation. The entry point and trajectory to the hematoma will be determined on a routine presurgical BrainLab® neuro-navigation planning station (BrainLab®, Munich, Germany) or an equivalent neuro-navigation planning station (e.g. Medtronic Stealth planning station, Fig. 1a). The planned trajectory represents the shortest approach from the surface of the brain to the hematoma, ideally in adequate distance from functional (eloquent) areas of the brain. Surgery will be performed in an emergency operating theatre or a hybrid operation theatre equipped with intraoperative CT (in hybrid OR), neuronavigation, and neuro-endoscopy. Neuro-navigation will be used to mark the skin incision and the exact location of the entry burr hole (Fig. 1b). The burr hole will be drilled and a transparent trocar (ViewSite Brain Access System®, VycorMedical™, U.S.A or equivalent) will be used as a working channel for the endoscope and the suction device (regular suction device, Artemis®, Apollo®, or other suction devices, Fig. 1c and d). The position and progress of the trocar towards the hematoma cavity will be monitored with neuro-navigation. The endoscope (LOTTA® system, Karl Storz Endoscopes, Germany; Minop®, BBraun, Tuttlingen, Germany or equivalent) will be inserted into the trocar and tracked using neuro-navigation. Using the pre-planned trajectory, the hematoma will be entered. Using continuous suction and irrigation, the hematoma will be aspirated and wash out (Fig. 1e). Under visual control using the endoscope, the hematoma cavity will be continuously monitored and active bleeding areas will be irrigated or coagulated using the endoscopic coagulation device and Floseal®. After the hematoma cavity has been cleared, a final inspection under endoscopic visualization will be carried out (Fig. 1f). Thereafter, the wound is closed in standard neurosurgical fashion[37]. Directly after surgery, while

still intubated and sedated, patients will be transferred for a cCT in order to assess adequate hematoma evacuation. In a hybrid OR setting, the cCT will be performed directly in the operating theatre. If hematoma removal is found insufficient by the treating neurosurgeon, the patient will return to the operating theatre for further hematoma aspiration (using the same approach). After surgery patient's will be monitored and cared for in an intensive care/stroke unit. The patient will then be treated, according to the current guidelines for BMT in SSICH[12] (systolic BP <140mmHg, ICU care, controlling seizures and glucose levels).

[figure not shown]

Figure 1: Steps of the surgery: A) Planning of the access; B) Confirming the entry point; C) The burr-hole access; D) Working with the suction device and the endoscope; E) suction of hematoma; F) completely evacuated hematoma cavity

3.4.2 Control group

The control group will receive the current gold standard treatment for SSICH according to the guidelines (BMT)[12]. This involves strict blood pressure control (SBP<140mmHg), if needed with intravenous or intraarterial blood pressure lowering agents, reversal of anticoagulation if applicable, intensive care surveillance and nursing on a ICU or stroke unit, control of seizures as well as glucose levels as needed and neurointensive monitoring if deemed necessary[12].

4 STUDY POPULATION AND STUDY PROCEDURES

4.1 Inclusion and exclusion criteria, justification of study population

The study population consists of patients with spontaneous supratentorial ICH (SSICH) defined by the following inclusion criteria upon screening. In accordance with our power analysis, we plan to enrol a total of 200 patients (100 patients in the intervention group, 100 patients in the control group). The recruitment procedure is described in 4.2 “recruitment, screening and informed consent procedure”.

Inclusion criteria:

- Patient age ≥ 18 and <85
- Spontaneous supratentorial intracerebral hemorrhage (SSICH), defined as the sudden occurrence of bleeding into the lobar parenchyma and/or into the basal ganglia and/or thalamus that may extend into the ventricles confirmed by imaging
- SSICH volume ≥ 20 mL < 100 mL (measured using the formula $\frac{A * B * C}{2}$)
- Stable clot volume defined as absence of increase of $>33\%$ (as assessed using the formula $(A * B * C)/2$) of initial clot volume on follow-up imaging.
- A focal neurological deficit consisting of either
 - clinically relevant hemiparesis (≥ 4 motor points on the NIHSS for facial palsy, motoric upper and lower extremities combined)
 - clinically relevant motor or sensory aphasia (≥ 2 points on the NIHSS)
 - clinically relevant hemi-inattention (formerly neglect, 2 points on the NIHSS)
 - decreased level of consciousness ($GCS \leq 13$)
- Presenting GCS 5 – 15 (in intubated patients GCS assessment will be performed after Rutledge et al.[38] (Figure 2) or if impossible, the last pre-intubation GCS will be used)
- Endoscopic hematoma evacuation can be initiated within 24 hours after the patient was last seen well/symptom onset
- Informed consent of patient (only for patients able to consent)

Exclusion criteria:

- SSICH due to known or suspected (on CT-A scan) structural abnormality in the brain (e.g. vascular malformation, aneurysm, AVM, brain tumor) and/or brain trauma and/or hemorrhagic conversion of an ischemic infarction
- Multiple simultaneous intracranial hemorrhages (e.g. multifocal ICH, cSDH, aSDH, SAH)
- Infratentorial hemorrhage or midbrain extension/involvement of the hemorrhage
- Coagulation disorder (including anticoagulation) with an INR of >1.5 which cannot be pharmacologically reverted until the planned time of evacuation
- Positive history of current pregnancy or breast-feeding in premenopausal women
- Relevant disability prior to SSICH (mRS >2)

- Any comorbid disease or condition expected to compromise survival or ability to complete follow-up assessments through 180 days (e.g. bilateral fixed dilated pupils)

GCS Motor Score	GCS Eye Score			
	1	2	3	4
1	1	1	1	2
2	1	1	1	1
3	1	1	1	2
4	2	1	2	2
5	3	2	3	3
6	4	4	4	5

JOURNAL OF TRAUMA AND ACUTE CARE SURGERY

Figure 2: GCS score in intubated patients after Rutledge et al.

4.1.1 Rationale for the inclusion of vulnerable patients

Concerning vulnerable patients, which we might have to include in this study due to the nature of SSICH being a medical emergency, the following applies:

These participants can be included in this study according to the above-mentioned inclusion and exclusion criteria. Since this study is based on an emergency setting, time is of vital importance. For participants not able to consent, an independent physician (not involved with the study) will be consulted to confirm that the interest of the patient are preserved by participating in this study.. As soon as the participants are able to consent again, they will be retrospectively informed according to the process described in 4.2 and can decide upon further participation in this study. Likewise, in the case that an independent physician was asked to confirm that the interest of the patient were preserved and the patient remains unable to consent, a legal guardian or a relative will be informed and can decide upon further participation. Information process will be the same for the legal guardian or relatives as described in 4.2 "Recruitment, screening and informed consent procedure".

If unresponsive participants or participants incapable of judgement show any sign that they are unwilling to participate in this study, they will be excluded from this study.

4.2 Recruitment, screening and informed consent procedure

The recruitment will take place at either the emergency department or the Stroke Centre of the University Hospital Basel. Participants will be recruited by a member of the study team in the form of consecutive ongoing enrolment in daily practice as well as recruitment through a referring family physicians or peripheral hospitals to the emergency department in daily practice.

Initial screening according to the eligibility criteria pre-specified above will be performed upon admission. Some of the inclusion measurements are used in daily practice (e.g. NIHSS, GCS score evaluation, admission-imaging scan) and must be applied before informed consent is given as this is necessary to determine an underlying disease and assess study eligibility of the respective participant. These measurements serve only for the standard clinical examination used in daily emergency room practice and for testing inclusion criteria for the present study. A specific clinical examination will be performed after informed consent by the patient, a legal guardian or an independent physician was given. The investigators, a member of the study team or the attending neurosurgeon in case none of the previously named persons is available, will explain to each participant the nature of the study, its purpose, the procedures involved, the expected duration, the potential risks and benefits and any discomfort it may entail. Each participant will be informed that the participation in the study is voluntary and that the participant may withdraw from the study at any time and that withdrawal of consent will not affect the participant's subsequent medical assistance and treatment.

The participants will be informed that the participants medical records may be examined by authorised individuals other than their treating physician.

All participants will be provided with a participant information sheet and a consent form describing the study and providing sufficient information for the participants to make an informed decision about the participation in the study. Enough time needs to be given to the participant to decide whether to participate or not, even in the setting of an emergency. However, since rapid evacuation is a vital asset of this study, we will limit this timeframe depending of the acuteness of the individual situation. The formal consent of a participant using the approved consent form, will be obtained before the participant is submitted to any study procedure aside the already mentioned necessary routine examinations of daily practice at our institution.

The consent form will be signed and dated by the investigators, a member of the study team or the attending neurosurgeon at the same time as the participants. A copy of the signed informed consent will be given to the study participants. The consent form will be retained as part of the study records and the informed consent process will be documented in the electronic patient file. All further study procedures will be commenced after the participants consented to participate in this study.

In case the patient is unable to consent due to impaired consciousness (i.e. due to the hematoma), an independent physician (who is not participating in the trial) will be asked to confirm whether the interests of the patient are preserved in the study or not. As soon as the patient regains the ability to consent, he will be retrospectively informed about the nature of the study, its purpose, the procedures involved, the expected duration, the potential risks and benefits and any discomfort the study may entail. The patient will then retrospectively be asked to provide informed consent to further participate in the study. In case a patient remains unable to consent or becomes permanently unable to consent, a legal guardian or relative will be informed about the study and will be asked to provide retrospective consent as proxy for the patient.

There will be no compensation for the participants in this study.

4.3 Study procedures

The planned overall study duration including recruitment period and follow-up for each participant is limited to 6 months after first admission to the hospital ending with visit 6. The study schedule consists of 6 study visits (V1-V6), which follow the regular in- and outpatient visit schedule in patients with SSICH (clinical routine), including the following procedures with the respective time period mentioned. All data collection for this study will begin after informed consent was given.

All imaging studies, study visits, the neurological examinations (GCS, NIHSS, MOCA) and the clinical examination are part of the daily clinical practice routine for SSICH, while the study specific examinations will consist of mRS evaluation, assessing the quality of life, patient satisfaction (Appendix 2) and acquiring blood samples. Blood sample will consist of collecting an aliquot of approximately 2 x 5 ml blood serum at each indicated visit. The additional blood samples for the study will be taken, if possible, during daily routine while the patient will be in the hospital (V1 & V3). For the Follow-Up visit (V6), an additional puncture will be necessary to obtain the blood samples. The PROMs Quality of Life and patient satisfaction will be assessed additionally by providing a paper-form questionnaire to the patients and their relatives. If patients are not able to complete the questionnaire, relatives will be asked to provide data.

Collected data will be preserved in encoded form to be used in future studies, patients will be informed about the encoded retention of data and given a separate informed consent. All blood samples will be discarded after analysis and will not be used for future studies.

We designed this trial together with affected patients, caregivers and patient organization representatives (EUPATI-CH) in the scope of PPI as pragmatic as possible, meaning that all visits and procedures were meticulously evaluated. With this we are convinced, that patients will remain in the trial as it is only little, if any at all, expenditure more than what would be the standard of care. From patients that drop out, we will analyse the data until the point of drop-out (last visit present) in an intention-to-treat fashion. Likewise, if any deviation from intervention protocol should occur, the results will be analysed as intention-to-treat. Outcome data collected for drop-

outs will consist of all study data collected to the last visit.

4.3.1 V1: Study inclusion, baseline assessment and treatment: up to 24 hours after symptom onset

Study eligibility criteria are confirmed and written informed consent is obtained from the patient. After informed consent was given, randomisation to the intervention or the control group will be conducted by a member of the study team through the CDMS SecuTrial®.

A clinical examination is performed including vital signs (resting blood pressure and heart rate, height, and weight), NIHSS, GCS, and mRS. Blood sampling for biomarkers will be obtained. Patient baseline data is acquired.

In the intervention group a study baseline CT scan (stability scan) is obtained 6 hours after the admission scan if surgical hematoma evacuation is started >6 hours after the admission scan. Endoscopic hematoma evacuation must be initiated within 24 hours according to the procedure described in 3.4.1 “Intervention group”. Surgical Baseline data is acquired.

Patients randomised to the control group will receive standard medical care according to the current guidelines as described in 3.4.2 “control group”.

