4.3.6 V6: Month 6 assessment: 6 months ± 7 weeks after treatment

Clinical examination is performed as detailed for V1 except for body weight and height and mRS. Blood sampling for biomarkers will be obtained. A cCT will be performed for all patients (control and intervention group) to evaluate possible rebleeding, hematoma resorption and the shape of the hematoma cavity. A MOCA Test is performed. Additionally, a questionnaire regarding patient satisfaction will be filled-out whenever possible through a relative or otherwise together with a member of the study team and patients and their relatives will be asked to fill out a questionnaire together with a member of the study team regarding the quality of life. Additionally, patients are telephonically contacted by a study-team member (blinded to the allocation) to assess the mRS according to the form in Appendix 4.

Study period	Treatment Period				Follow-Up	
Visit	1	2	3	4	5	6

Time (hour, day, week)	<24 hours of symptom onset	24 hours after treatment onset	72 hours after treatment onset	7 days after treatment onset	3 months after treatment onset	6 months after treatment onset
Eligibility	X					
Study consent	X					
Asses vital signs (BP,HR,height)	X	X	X	X	X	X
Acquire NIHSS score	X	X	X	X	X	X
Acquire GCS score	X	X	X	X	X	X
Acquire mRS score	X	X	X	X	X**	X**
Acquire blood samples (NfL, GFAP, S100B, IL)	X		X			X
Conduct Stability CT scan*	X					
Conduct directly postoperative CT scan†		X				
Conduct postinterventional CT scan‡		X				X
Quality of Life					X	X
Patient Satisfaction					X	X
Cognition					X	X

*intervention group only; only required if surgery cannot be initiated within 6 hours after the first cCT scan

†intervention group only; the directly postoperative cCT is conducted directly after surgery to assess hematoma evacuation and differentiate potential recurrent hemorrhage

‡all patients; the postinterventional cCT scan is conducted 24 hours and 6 months after the treatment start to assess potential recurrent/enlarged hematoma and defect size

**blinded telephone assessment

4.3.7 Additional material, storage, concomitant care as well as methods and tests used for sample collection and analysis

The imaging analysis, the additional materials and biomarkers used for this study and the procedure to reverse oral anticoagulation are explained in the following section.

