4.3.7.1 Imaging analysis

In this study we will conduct cCT scans:

- At admission (clinical routine, both groups)
- 6 hours after the admission scan if surgery is started >6 hours after the admission scan (clinical routine stability scan, intervention group only)
- Directly postoperative (clinical routine in this procedure, intra-operative or directly after surgery, intervention group only)
- At the first day after start of treatment (clinical routine in SSICH, both groups)
- At the visit after 6 months (clinical routine, both groups)

The cCT scans serve to assess the hematoma volume and to provide information about the hematoma reduction rate or increase in hematoma volume and possible rebleeding after surgery.

The pre-operative hematoma will be assessed with the $\frac{A * B * C}{2}$ formula for screening purposes due to its fast and broad applicability in emergency room settings and will then, in a second step, be validated with the neuronavigation software later on[34]. To analyse the often irregular-shaped and small postoperative hematoma volume (cCT scan directly after surgery (intervention)/ 24 hours after treatment onset(control)), the hematoma will be segmented, and its volume calculated manually on a BrainLab® planning station (or equivalent) by a trained member of the study team. Both hematoma volumes as calculated on the BrainLab® planning station (or equivalent) from cCTs at admission and directly postoperative/after 24 hours after treatment onset will be compared to assess the evolution of the hematoma volume. This increases the comparability as the $\frac{A * B * C}{2}$ formula struggles with small irregular shaped hematoma volumes.

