4.4 Withdrawal and discontinuation

Participants, their respective legal guardian or next of kin in case the patient remains unable to consent, can withdraw informed consent for this study whenever they want. They are withdrawn from this study if they do not meet the inclusion criteria mentioned under 4.1 “Inclusion criteria”. If patients of childbearing age get pregnant during the course of this study, they will be converted to MRI imaging instead of CT imaging but will not be ruled out.

The data of participants withdrawing prematurely (e.g. withdrawal of informed consent) is vital for the validity of the results of this trial. Currently, no sufficiently powered studies have been published on the potential benefits of ES in SSICH and it will be crucial to analyse every last patient so that the conclusion drawn from this trial is based on best possible evidence from our sample. With that, we can guarantee that future patients receive treatment based on the best possible data. The data and biological material of patients withdrawing prematurely will remain coded and used for the final outcome analysis according to the intention-to-treat principle. Participants lost that way will be marked as lost to follow-up.

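### Clot stability is an inclusion criterion for all, but the only scheduled pre-treatment scan that could test it follows allocation in the ES arm only, and 4.4 allows withdrawal after randomisation

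*Protocol*

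**What the plan says.** - **The criterion.** The synopsis and Protocol 4.1 list "Stable clot volume defined as absence of increase of" more than 33% of the initial volume, judged on follow-up imaging. It applies to all patients.
- **Order of events.** Protocol 3.3.3 on randomisation: "This process will take place 1) after enrolment criteria were met". Section 4.3.1 has eligibility confirmed, then: "After informed consent was given, randomisation to the intervention or the control group will be conducted". The stability scan comes later in the same section: "In the intervention group a study baseline CT scan (stability scan) is obtained 6 hours after the admission scan", on condition that evacuation starts more than 6 hours after the admission scan.
- **Who is scanned.** The footnote to the schedule (4.3.6, repeated in Appendix 1) reads "intervention group only; only required if surgery cannot be initiated within 6 hours after the first cCT scan". The imaging list in 4.3.7.1 reads "clinical routine stability scan, intervention group only". After admission, the first scheduled CT in the BMT arm is the one at 24 ± 6 hours after start of treatment (4.3.2). All patients have it, and its stated purpose is to follow the haematoma volume.
- **Withdrawal.** Section 4.4: "They are withdrawn from this study if they do not meet the inclusion criteria mentioned under 4.1". No time limit is given. The next paragraph deals with premature withdrawal, naming withdrawn consent as an example. It keeps the data for the intention-to-treat analysis and ends: "Participants lost that way will be marked as lost to follow-up".
- **Drop-outs and missing data.** Section 4.3 analyses drop-outs up to the last visit present. Section 5.2 uses multiple imputation only if more than 5% of patients, across arms, lack the primary outcome.

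**The concern.** An inclusion criterion should be settled before allocation, on information gathered in the same way in both arms. Here the only scheduled scan before treatment that could settle it depends on the arm, so it must follow allocation. For any patient whose stability is judged on that scan, the order in 3.3.3 cannot hold.

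The conflict matters because of 4.4. A team that finds more than 33% growth on the planning scan has a patient who no longer meets an inclusion criterion, and a sentence that says such patients are withdrawn. The trial is open-label, so the team knows the arm. The background section says larger haematomas have poorer outcome, so the patients at risk of being lost would tend to have a poorer prognosis. A patient withdrawn on the first day contributes no 6-month mRS. The comparison of good-outcome rates would then no longer rest on the randomised groups.

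**Working it through.** **1. The sections side by side.**

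| Question | ES arm | BMT arm |
|---|---|---|
| Stability required? | Yes (4.1) | Yes (4.1) |
| Scheduled scan between admission and treatment | Only if surgery starts >6 h after the admission scan (4.3.1, 4.3.7.1) | None |
| Timing relative to allocation | After | – |
| Next scheduled CT | Directly after surgery, then 24 ± 6 h | 24 ± 6 h after start of treatment |
| Withdrawal for unmet inclusion criteria | No time limit (4.4) | No time limit (4.4) |

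**2. Does the intention-to-treat wording protect the 6-month outcome?** Not by itself. Sections 4.3 and 4.4 keep data already collected, whereas the primary outcome is collected at 6 months. The imputation trigger may not be reached: 10 of 100 ES patients lost out of 200 is 10/200 = 5%, which is not more than 5%.

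**3. Size of a one-sided loss.** From the protocol: 50% good outcome under BMT. Assumed, because the protocol gives no figures: no true effect, a share g of the ES arm lost, and a good-outcome rate r among those lost.

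ES rate among those kept = (0.50 − g·r)/(1 − g). The BMT odds are 1, so OR = rate/(1 − rate).

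| g | r | ES rate kept | OR |
|---|---|---|---|
| 5% | 30% | (0.50 − 0.015)/0.95 = 0.511 | 1.04 |
| 5% | 10% | (0.50 − 0.005)/0.95 = 0.521 | 1.09 |
| 10% | 30% | (0.50 − 0.03)/0.90 = 0.522 | 1.09 |
| 10% | 10% | (0.50 − 0.01)/0.90 = 0.544 | 1.20 |
| 20% | 30% | (0.50 − 0.06)/0.80 = 0.550 | 1.22 |
| 20% | 10% | (0.50 − 0.02)/0.80 = 0.600 | 1.50 |

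Here g is a share of the whole ES arm, while only patients operated on more than 6 hours after the admission scan are scanned. If half the arm were scanned (assumption), g = 10% needs growth above 33% in 0.10/0.50 = 20% of those scanned, and g = 20% needs 40%.

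**4. Effect on the stopping rule.** The Bayes factor was computed with standard normal priors on the average log odds and on the log odds ratio. These are assumed to be the package defaults, which the protocol does not print. As a check, at 50% against 80% with looks every 5 per arm from 10 per arm, 89.6% of 800 simulated trials reached a Bayes factor of 10 by 70 per arm. The protocol states about 90%.

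With looks at 40, 60, 80 and 100 per arm and no true effect, the chance of a Bayes factor of at least 10 in favour of ES was:

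- about 0.6% if every patient is kept
- 1.7–3.6% if 10% of ES is lost (r from 30% down to 10%)
- 3.6–11.5% if 20% of ES is lost

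**5. If 4.4 is also applied to the 24-hour CT.** Equal loss with equal r gives the same rate in both arms and OR 1.00. If BMT lost 20% and ES 10%, with r = 10%, the rates would be 0.600 and 0.544, and the odds ratio for ES (0.544/0.456)/(0.600/0.400) = 0.80. The direction depends on how 4.4 is applied.

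**The case against.** A reader might infer that the protocol orders expanding haematomas to be removed from ES and never from BMT. The text does not go that far, for four reasons.

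- No sentence says that growth on the stability scan triggers withdrawal. Section 3.4.1 gives the scan's use as surgical planning, and 4.3.1 has eligibility confirmed before randomisation. On a fair reading, eligibility is closed by then and the later scan only guides surgery.
- The lost-to-follow-up sentence closes a paragraph about premature withdrawal such as withdrawn consent. The ineligibility sentence stands in the paragraph before. The protocol also stresses analysing every patient, and 5.2 has staff seek missing data from the patient, relatives or treating physician.
- Section 4.4 names no arm, and 4.1 does not define follow-up imaging as the stability scan. Read literally enough to withdraw ES patients, 4.4 could also withdraw BMT patients whose growth appears on the 24-hour CT.
- The sizes above rest on assumed rates. Nor can it be said that imputation would draw on the better-prognosis ES patients who remain, because the protocol gives only the trigger and not the model.

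These points stand, and they limit certainty, direction and size. They do not remove the conflict over when stability is judged, the absence of a time limit on withdrawal in 4.4, or the restriction of drop-out data to the last visit. The benign reading is one that the protocol allows but does not state.

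**Conclusion.** The protocol makes clot stability a condition of entry for all, but schedules the only pre-treatment scan that could test it after allocation, in one arm, for part of that arm. With 4.4 and the drop-out rule in 4.3, it permits a post-randomisation, prognosis-related loss of the primary outcome that can differ by arm. It does not order that loss.

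Before treatment only ES patients can be affected, so bias in favour of ES is the likely direction. It is not certain, because 4.4 could also be applied to the 24-hour CT. The size is unknown. The illustrative odds ratios of 1.04–1.50 assume no true effect, 50% good outcome, loss from ES only of 5–20% of the arm, and 10–30% good outcome among those lost. The upper end needs a large share of ES patients to be scanned and withdrawn.

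**What to change.** Reconcile 3.3.3, 4.1, 4.3.1, the schedule (4.3.6 and Appendix 1), 4.3.7.1 and 4.4:

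1. State that eligibility, including clot stability, is settled before randomisation by the same rule in both arms.
2. Limit the withdrawal rule in 4.4 for unmet inclusion criteria to the time before randomisation.
3. State that growth on any later scan, in either arm, never removes a patient from follow-up or from the intention-to-treat analysis, and that the 6-month telephone mRS is obtained and analysed in the assigned arm.

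How a patient with growth on a later scan is treated stays a clinical decision, and the change does not touch it.

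The cost is mainly protocol wording, plus 6-month telephone assessments for patients who might otherwise have been withdrawn. There is a small downside: some patients whose clots later prove unstable remain in both arms, and stability cannot be checked in those with only an admission scan before randomisation. The criterion should say how such patients are classed.
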